3.7 Exclusion Criteria

1. Substantial comorbid injury (e.g., long bone fracture)
2. Pregnancy/breastfeeding
3. Prisoner status
4. Chronic daily opioid use prior to MVC (>20 mg oral daily morphine equivalents)
5. Active psychosis, suicidal ideation, or homicidal ideation
6. Plans for hospital admission
7. Known chronic kidney disease, stage 4 or higher ($GFR \leq 29$)
8. Intubated and sedated at time of enrollment
9. Inability to provide informed consent (receipt of sedative, hypnotic agent making the patient non-decisional for consent)
10. Known hypercalcemia
11. Vitamin D supplements in excess of 800 IU daily

12. Any other history or condition that would, in the site investigator's judgement, indicate that the patient would very likely be non-compliant with the study or unsuitable for the study (e.g., might interfere with the study, confound interpretation, or endanger patient)

3.8 Subject Recruitment and Screening

Prior to approaching the participant, medical history data will be reviewed for information pertaining to inclusion/exclusion criteria in section 3.6 and 3.7. If the participant is determined to be ineligible, the review will stop. The purpose of assessing this information is to approach only those patients who are potentially eligible. Record will be kept of patients who are screened but excluded and for what reason. A HIPAA waiver will be requested to permit the review of medical record data for evident exclusion criteria prior to approaching a participant (this will reduce study burden on the study population). In participants who otherwise appear to be eligible for the study, the attending physician/medical record will be consulted to determine if admission is planned (most of the time this can be determined through chart review). Reasons for exclusion will be recorded. To be eligible for the study, during ED admission pain severity must be at least 4/10 or higher). Participants will be approached by study personnel and will be offered participation. Participants will undergo informed consent with enrolling RAs in the ED. Participants will receive paper copies of their main study consent, HIPAA authorization, biospecimen collection and social security collection forms. Both the participant and consenter will open and review the documents. Because both the RA and the participant will have forms open, the participant will follow along on paper while the consenter explains each section. After reviewing the consent documents, if the potential participant is willing to participate, the consenter and participant both sign the consent forms and the RAs will enter their time and date of their signature in REDCap. Once all fields are complete, then a copy of the completed consents (Main Study Consent, HIPAA Authorization, Biospecimen Collection and SSN Form) are given to each the participant and the consenter. The consenter will then save a scanned copy of the forms to REDCap, the central and secure online study database.

If participant refuses consent, data collected to that point will be retained to describe the proportion of MVC patients who were screened but refused to participate (we will maintain demographic information for audit purposes). Reason to refuse participation will be also documented and retained.

If the participant is after 10 days following their last menstrual period, and is not on birth control, a urine pregnancy test will be performed prior to randomization. If the participant is found to be pregnant, they will be excluded from the study. Once participants are determined to meet full inclusion criteria and have no reason for exclusion, consented participants will be randomized and study drug will commence on enrollment in the study. Participants who are initially intubated may be eligible for the study, as long as they are extubated, alert, and oriented at the time of consent, enrollment and other eligibility criteria are met.

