3.2 Study Overview

Described the sequence of events in recruiting 90 patients in a multi-center randomized controlled trial. To assess a key primary outcome, we will enroll 50% white and 50% black MVC into the study. Each participant will be screened in based on a point of care Vitamin D test. This will be performed at the time of screening. Individuals with a Vitamin D level <100 ng/ml will be enrolled. Patients will be randomized 1:1 to receive a single dose of 300,000 IU of ergocalciferol versus placebo and followed for 3 months. At 3 months, patients will send a blood sample easily collected at home on a blood spot card to assess Vitamin D level 3 months following injury which is a key feasibility primary outcome.

Patients presenting to the ED within 24 hours of MVC (n=90, 45 non-Hispanic Black, and 45 non-Hispanic White) will receive a single dose of study drug prior to ED discharge (1:1 allocation 300,000 IU ergocalciferol or placebo). Prior to study drug administration, a baseline assessment will be performed (see below), and a fingerstick blood sample will be obtained to evaluate 25-hydroxyvitamin D level. Online survey follow-ups assessing primary and secondary outcomes and potential adverse events will be performed 3 weeks, 6 weeks, and 3 months after ED enrollment by study RAs using web-based REDCap™ software. Participants will also complete brief “flash-surveys” at the 2-week, 4-week, and 5-week timepoints using REDCap survey links. At 3 months, participants will also perform a fingerstick blood collection at home and mail the sample in a prepaid envelope to a lab to be processed to enable assessment of 3 month 25-hydroxyvitamin D concentration by treatment group.

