3.6 Inclusion Criteria

1. ≥ 18 years and ≤ 65 years of age
2. Admitted to ED within 24 hours of motor vehicle collision
3. Plan to discharge to home from the emergency department
4. Stated willingness to comply with all study procedures and availability for the duration of the study (with the exception of the blood draw sample collected in the ED, which is optional)
5. Has a smartphone with continuous service ≥ 1 year
6. Able to speak and read English
7. Alert and oriented, and capable of engaging in informed consent
8. Willing to take on-time dose of study medication (2 capsules of Vitamin D or placebo)
9. Non-Hispanic white or non-Hispanic black
10. Point of care Vitamin D level <100 ng/ml
11. During ED admission pain severity must be at least 4/10 or higher

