5.1 Enrollment Procedures

This first visit will take place upon admission to the hospital following MVC within 24 hours of the collision. Patients who meet inclusion criteria/exclusion criteria based on a review of the electronic medical record by research assistants, participants will be approached for participation. If the patient is interested in participating, they will then undergo informed consent. At this point in time, the participants will undergo baseline assessments (administered through REDCap) and collections of point of care Vitamin D levels with blood spot card. The participants will also have the option to consent to collect additional blood during a standard of care procedure while in the ED. The study would collect an EDTA tube,

a sodium heparin tube, and PAX gene RNA and DNA tubes. Patients with a Vitamin D level <100 ng/ml, will then take the baseline questionnaire. After all baseline data is collected, participants will be randomized and then administered appropriate study medication (Vitamin D or placebo). This administration will be documented in the MAR. Patients will be given a paper copy of their consent. Upon discharge of the patient, the patient will be given supplies to perform a home fingerstick blood draw (similar to one collected in the ED for baseline) and blotting on a blood spot card, which will occur at the 3-month timepoint.

Medical record information abstracted at time of admission will include information related to patient past medical history and initial motor vehicle collision care, and medication use prior to admission and prior to enrollment. Laboratory values relevant to patient renal and hepatic function will also be recorded (if obtained) along with any toxicology labs obtained by the primary treating team.

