7.5 Stopping Rules

The entire trial will stop if 3 or more patients have severe adverse events of grade 3 (severe) or higher severity per the CTCAE scale that is related or possibly related to study participation, or any investigator judges it necessary for medical, safety, regulatory, or other reasons consistent with applicable laws, regulations, or good clinical practice. Patients who decline further participation and patients experiencing adverse effects that in the opinion of study investigators indicate that study drug should be stopped will be discontinued from study medication. Criteria for stopping the study trial among individual participants for review are shown in Appendix 1.

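### The only pregnancy test in the plan is waived for anyone on birth control, so an unrecognised pregnancy can be randomised and given the single dose

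*Combined protocol and SAP*

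**What the plan says.** Section 3.7 lists "Pregnancy/breastfeeding" among the exclusions, with no qualifier and no statement of how pregnancy is to be ascertained. Section 3.6 admits participants "≥ 18 years and ≤ 65 years of age", so people of childbearing potential will be enrolled.

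The method of ascertainment is in Section 3.8. If the participant is "after 10 days following their last menstrual period, and is not on birth control, a urine pregnancy test will be performed" before randomisation. The next sentence gives the consequence: "If the participant is found to be pregnant, they will be excluded from the study".

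Section 3.8 also says that, before anyone is approached, "medical history data will be reviewed for information pertaining to inclusion/exclusion criteria in section 3.6 and 3.7". Section 5.1 then takes the participant through consent, baseline assessments, the point-of-care vitamin D test and the questionnaire to randomisation and dosing. It does not mention a pregnancy test.

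On treatment, Section 3.2 states: "Patients will be randomized 1:1 to receive a single dose of 300,000 IU of ergocalciferol versus placebo". Sections 4.2 and 5.2 make this one observed administration in the emergency department.

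**The concern.** The exclusion and the check that enforces it do not cover the same people. The exclusion applies to every pregnant participant. The test applies only to those who are both past day 10 and not using birth control. Birth control is not defined by method, adherence or verification, so a bare self-report is enough to waive the test.

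A site that follows the plan exactly can therefore randomise and dose a participant whom Section 3.7 means to keep out, without any protocol deviation. The timing makes this matter. Section 7.5 provides that participants with adverse effects that "indicate that study drug should be stopped will be discontinued from study medication", and Section 7.6 speaks of reducing or holding doses. Neither can act once the only dose has been swallowed. Sections 1.2 and 1.4 describe this dose as keeping 25-hydroxyvitamin D above 30 ng/ml for over 3 months, so its effect does not pass quickly either. For an unrecognised pregnancy, the exclusion can be applied only before randomisation.

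**Working it through.** The plan gives no figure to reproduce. The check is a reading of the rule, a search for any other safeguard, and simple arithmetic on scale.

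**Step 1: the rule as a logical condition.** Let A be more than 10 days since the last period and B be not on birth control. Section 3.8 requires a test if A and B both hold.

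| More than 10 days since last period | On birth control | Test required |
|---|---|---|
| Yes | No | Yes |
| Yes | Yes | No |
| No | No | No |
| No | Yes | No |

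The second row is the gap, and it has no upper limit on time. As an illustration, a participant on birth control at 49 days since her last period is 49 − 10 = 39 days beyond the rule's own threshold and still exempt. The third and fourth rows are the lesser concern, because pregnancy is less likely soon after a period.

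**Step 2: other places where pregnancy might be detected.**

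- Section 3.7, item 2: states the exclusion but gives no means of finding it.
- Section 3.7, item 12: allows exclusion on the investigator's judgement, which needs something to prompt it.
- Section 3.8, record review before approach: finds what is already recorded.
- Section 3.8, requirement that no exclusion applies before randomisation: depends on what the earlier steps revealed.
- Section 5.1 and Table 2: list no pregnancy test. The laboratory values abstracted under 5.1 are renal, hepatic and toxicology results, taken only where the treating team obtained them.
- Section 7: counts a congenital anomaly as a serious adverse event but sets out no steps for a pregnancy discovered after dosing.

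None of these reliably detects a pregnancy that the participant does not know about.

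**Step 3: expected number of cases.** Write it as E = 90 × f × c × p, where f is the proportion of women, c is the proportion of those women who are of childbearing potential and exempt through birth control, and p is the prevalence of unrecognised pregnancy among them. The documents give none of f, c or p, so E cannot be computed. For scale, assume f between 0.40 and 0.60:

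- 0.40 × 90 = 36 women; 0.60 × 90 = 54 women.
- Even if every one of them were exempt (c = 1), E would reach 1 only if p were 1/54 = 1.9% (with 54 women) or 1/36 = 2.8% (with 36). With c below 1, p would have to be higher.

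**Step 4: chance of active exposure, given k such participants.** With 1:1 allocation and assignments treated as independent, P(at least one receives active drug) = 1 − 0.5^k.

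- k = 1: 1 − 0.5 = 0.50
- k = 2: 1 − 0.5² = 0.75

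Section 4.3 assigns by minimisation on race, sex and pain score, so assignments are not strictly independent and 0.75 is approximate. Both figures are conditional on such participants being enrolled and say nothing about how likely that is.

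**Step 5: ceiling on the testing burden.** Under the same assumption on f, testing every woman would take 36 to 54 tests in all. The added number is smaller, because some women are tested under the present rule and some, at ages up to 65, are not of childbearing potential.

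**The case against.** The best defence is that this is deliberate risk-tiering. The rule tests the group at highest risk and spares two groups at lower risk. If a recent period is an acceptable reason not to test, contraception may be one too. The documents do not say that a single 300,000 IU dose harms a fetus, and they describe the dose as very well tolerated. The number of affected participants is unknown and probably small. In a single-dose trial, stopping drug cannot undo any exclusion discovered late: hypercalcaemia and advanced kidney disease are screened only when already known. An investigator could also act under item 12 if a contraceptive user reported a late period. The consent form is not among the pages available, so any wording there on pregnancy cannot be checked.

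Much of this stands. The risk is unquantified, no fetal harm is documented, and the 0.50 and 0.75 only restate the allocation ratio. The point is not an internal contradiction and does not touch the analysis.

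It does not remove the gap. The kidney and calcium exclusions are limited to known disease in their own wording, whereas the pregnancy exclusion is not, and the plan has already chosen to enforce it by testing. The two waivers also differ: the cycle-timing one is bounded at 10 days, while the birth-control one has no bound and rests on an undefined report. Item 12 permits action on a suspicion but requires none, and it does not help where nothing is suspected. Sites may test more widely in usual care, but the protocol does not require it.

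**Conclusion.** The concern holds. As written, Section 3.8 never requires a pregnancy test for a participant on birth control, and nothing else in the available text reliably finds an unrecognised pregnancy before the only dose is given. The conclusion follows from the wording of the rule and depends on no statistical assumption.

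The size is modest. The probable number of cases is small, but that is a judgement, because the documents give no sex split, contraceptive use or pregnancy rate. The case for change rests on three facts: the plan excludes these participants outright, exposure cannot be withdrawn after dosing, and the remedy extends a test the protocol already uses. It is a safety improvement that should be made, and it does not threaten the validity of the trial's results.

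**What to change.** Replace the testing sentence in Section 3.8 with wording such as: *Every participant of childbearing potential will have a urine pregnancy test before randomisation, whatever her reported birth control or time since last period.* Keep the following sentence, which excludes anyone found to be pregnant. Because enrolment runs to age 65, add a short definition of childbearing potential, for example all female participants except those with documented sterilisation or menopause. Insert the test in the Section 5.1 sequence before randomisation.

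Removing the birth-control waiver is the essential part. Dropping the cycle-timing waiver as well gives staff one simple rule, but it could be kept if the sponsor prefers.

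The cost is one sentence and a definition in 3.8, one step in 5.1, and a modest number of extra urine tests, fewer than the 36–54 ceiling under the assumed 40–60% women. The work-up before randomisation already includes a fingerstick and questionnaires for everyone, so the added time should be short. Sample size, power and analysis do not change.

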3.9 Early Withdrawal of Subjects

3.9.1 When and How to Withdraw Subjects

Participants may withdraw from the study at any point in time if they no longer wish to participate in the study.

3.9.2 Data Collection and Follow-up for Withdrawn Subjects

If the patient voluntarily withdraws from the study, outcome measures from completed timepoints will be collected and included in intention to treat analysis. If the patient is lost to follow-up and is unresponsive to more than 3 phone calls and 3 secure e-mails, the next of kin listed in the medical record will be contacted once to attempt to reach the participant. If this is not successful, then 1 final email will be sent to attempt to contact the consented participant.

Study Drug

4.1 Description

The study drug is Vitamin D₂ (ergocalciferol) 300,000 IU administered orally as 2 capsules comprising approximately 150,000 IU each.

4.2 Treatment Regimen

Within 24 hours of presenting to the ED for a MVC, and immediately following enrollment in this study, participants will be provided with study drug or placebo. The study drug and placebo will be manufactured and encapsulated by a 503b compounding pharmacy (i.e., Pharmacy Innovations), and will ship the study drug to the investigational pharmacy at each study site. Immediately following randomization, the IDS pharmacy will receive an email with the unblinded treatment allocation for the participant. The IDS at each site will dispense the appropriate study drug once they receive a prescription from the clinician at enrollment. Study medications (placebo or active) will be administered orally via a one-time dose that will be observed by the research personnel in the ER.

4.3 Method for Assigning Subjects to Treatment Groups

Once a potential subject has been successfully screened, does not meet any exclusion criteria, is willing to participate in the study, and signs informed consent, the participant will be randomized by the study site using a minimization algorithm stratified on race, sex, and pain score. Randomization of participants using minimization will be accomplished using a centralized, web-based, validated (compliant with FDA 21 CFR Part 11) service (randomize.net). In this algorithm, a new participant is sequentially assigned to a particular treatment group by taking into account the covariates of the current and previously randomized participants. To further optimize power in this small, pilot study to examine the effect of race, and achieve a main goal of this study, a 1:1 ratio of non-Hispanic Black and White Americans will be enrolled. Once enrollment reaches 45 in a given race strata (e.g., non-Hispanic Black), enrollment for that race will cease. All participants, investigators, study

personnel, and follow-up team members will be blinded to allocation and concealment will be maintained throughout the study. Only the investigational pharmacy and study statistician will be unblinded to the drug the participant is receiving. They will not reveal this to the patient care team, investigative team, or to the participant. Dosing schedule, route of administration, number of pills in each dose, and the appearance of the capsules will be identical among each group.

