Safety and Adverse Events.....	16
7.1 Definitions.....	16
7.2 Recording of Adverse Events.....	18
7.3 Reporting of Serious Adverse Events and Unanticipated Problems	19
7.3.1 Investigator reporting	19
7.4 Unblinding Procedures.....	21
7.5 Stopping Rules.....	21
7.6 Medical Monitoring	21
7.7 Confidentiality.....	23
7.8 Source Documents.....	24
7.9 Case Report Forms (as applicable)	24
7.10 Records Retention.....	24
Study Monitoring, Auditing, and Inspecting	24
8.1 Study Monitoring Plan.....	24
8.2 Auditing and Inspecting	25
Ethical Considerations	25
Study Finances.....	25
10.1 Funding Source	25
10.2 Conflict of Interest	26

10.3 Subject Stipends or Payments.....	26
Publication Plan	26
Data Management Plan	26
References.....	27
Appendices.....	30
14.1 Appendix 1: Adverse Event Monitoring and Stopping Rules Table.....	30

List of Abbreviations

AE: Adverse Events
cc: cubic centimeters
CRF: case report form
DASS: Depression, Anxiety, and Stress Scale
DCC: data coordinating center
DNA: deoxyribonucleic acid
EC: ethics committee
ELISA: enzyme linked immunosorbent assay
FDA: Food and Drug Administration
g: grams
GFR: glomerular filtration rate
IDS: investigational drug services
IRB: institutional review board
IU: international units
MAR: medication administration record
MCS: mental component score
MSP: severe musculoskeletal pain
MOS: medical outcomes survey
MVC: motor vehicle collision
NRS: numeric rating scale
OT: occupational therapy
PCS: physical component score
PT: physical therapy
PTSD: post-traumatic stress disorder
RCT: Randomized Controlled Trial
RNA: ribonucleic acid
RPS: regional pain scale
SAE: serious adverse events
SF-12: short form 12 item questionnaire
TBSA: total body surface area
UNC: University of North Carolina
UPLC/ESI/MS/MS: Ultraperformance Liquid Chromatography/Electrospray Ionization Mass Spectrometry

Study Summary

Title	Randomized Controlled Trial of Vitamin D to reduce racial disparity in chronic pain following Motor Vehicle Collision
Short Title	VENTURE
IRB Protocol Number	21-2589
Phase	2
Methodology	Double Blind, Randomized Controlled Trial using a parallel design
Study Duration	2 years
Study Center(s)	University of North Carolina-Data Coordinating Center Rhode Island Hospital University of Massachusetts Washington University Cooper University Hospital

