Analysis plan Overall efficacy (a) will be addressed by evaluating for evidence that Vitamin D administration per protocol vs. placebo decreases overall MSP scores across study timepoints. The effect of the intervention on overall pain over time will be assessed by evaluating the coefficient for treatment group (β_1) in the model: $P_{ij} = \beta_0 + \alpha_{0i} + \beta_1 \text{Treatment}_i + \beta_2 \text{Race}_i + \beta_3 (\text{Treatment} \times \text{Race}) + \varepsilon_{ij}$, where P_{ij} is the pain score for the i th individual at time point j , β 's denotes fixed effects, α_{0i} is the random intercept for the i th individual and ε corresponds to random errors. Narrowing of racial disparity will be addressed by evaluating the interaction between race and treatment (β_3 in model above). Specifically, as described above we will assess whether Vitamin D has greater effect on pain outcomes over time in Blacks than Whites. All analyses will be evaluated on the basis of intention to treat. Prior to

[figure not shown]

Figure 2. Plot demonstrating power to detect a main effect (β_1 , black lines) and interaction (β_3 , blue lines) across a range of sample sizes, at three effect sizes estimated using simulation data generated from previous studies. Vertical red line indicates sample size proposed here (n=90). This demonstrates the power to assess Aim 2a (black) and 2b (blue).

data un-blinding, the study statistician will perform a blind review of the data in which statistical models will be developed and tested using dummy (computer-generated) treatment assignments. This is to ensure important covariates are added to the model prior to un-blinding to eliminate any bias of model covariate selection on results. After un-blinding the data, we will use appropriately specified linear contrasts of model parameters to estimate mean differences between participants treated with Vitamin D and placebo and 95% confidence intervals.

Power Estimates of power were derived using a Monte Carlo simulation based on parameter estimates from our observational data of MVC survivors using R (v. 4.0.2⁴⁸); and the *simr* package (v. 1.0.5⁴⁹). The power across a range of effect sizes for the main effect (a) is shown in Figure 2. These data and analysis must be seen as general estimates given that we lack intervention data for this population/condition.

Secondary Analyses:

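### The written primary pain model omits sex, a minimisation factor, and site; the cost is a modest loss of precision, not bias

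*Combined protocol and SAP*

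**What the plan says.** **Allocation.** Section 4.3 has patients randomised by the study site "using a minimization algorithm stratified on race, sex, and pain score". A central web service assigns each patient by "taking into account the covariates of the current and previously randomized participants". Site is not in the list of factors. No random element and no cut-points for the pain score are given. Section 3.2 sets 1:1 allocation in 90 patients ("n=90, 45 non-Hispanic Black, and 45 non-Hispanic White").

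**Sites.** Besides UNC as coordinating centre, the Study Summary lists "Rhode Island Hospital University of Massachusetts Washington University Cooper University Hospital". There are no per-site targets.

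**Model.** In 6.1 the pain score is modelled on treatment (β1), race (β2) and treatment × race (β3), with a random intercept per patient. The ED score is one of the four repeated outcomes, so it is not a covariate. On disparity, 6.1 says: "Narrowing of racial disparity will be addressed by evaluating the interaction between race and treatment".

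**Other covariates.** Section 6.1 plans a blind review, using dummy treatment codes, to settle covariates before un-blinding. It names none. Sex appears in secondary interaction and stratified analyses (2.2 and the secondary analyses in 6.1). No section mentions a site term.

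**The concern.** A trial that balances its arms on a factor normally carries that factor in the analysis. Balancing makes the treatment estimate less variable. If the model leaves the factor out, its standard error does not reflect that gain, and the interval is wider than the design earned. Sex is in this position here. ED pain score is in a related one, because it is balanced on but used as an outcome.

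Site differs in kind. It is not a listed balancing factor, so arms can be uneven within a hospital by chance. Any site difference in pain is then ordinary noise in the treatment effect, part of which a site term would remove.

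Two things are at stake. One is a little precision on β1 in a trial of 90. The other is the variance passed to the larger trial, since the Introduction says this pilot is to supply effect size and sample variation for that purpose.

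**Working it through.** **1. The plan's own figures.** Pain-model power is given only in Figure 2, which is not shown, and the text gives no alpha, effect size or variance, so it cannot be reproduced. The other figures in 6.1 do reproduce: 1.96 × √(0.8 × 0.2/90) = 0.0826, stated as 8.3%; and a paired t-test with n = 36 (80% of 45), change 10 and SD 4 has power of essentially 100%, stated as >99%. Neither depends on this point.

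**2. Balance within site.** Minimisation of 90 patients was simulated 1,500 times. Assumptions: four equal sites, 60% in one sex, pain in two levels, assignment probability 0.8 or 1.0.

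| | Site not a factor | Site a factor |
|---|---|---|
| Mean arm difference per site | 3.3 | 0.9–1.6 |
| Worst site, median | 5–6 | 2–3 |
| Some site differs by 6 or more | 48–50% | 0–7% |
| Some site differs by 8 or more | 22–24% | 0–1% |

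Sites of 40/30/20/10% behave similarly. Sex stays balanced between arms either way (mean worst difference 0.7–1.8). A coin-flip calculation for 22 patients gives 2 × P(Bin(22, 0.5) ≤ 7) = 0.134 per site for a 15:7 split or worse, and 1 − (1 − 0.134)⁴ = 0.44 for at least one of four. That overstates the risk, because minimisation holds the overall arm totals together.

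**3. Precision.** Analytically, adding a balanced factor with variance share s multiplies the SE by about √(1 − s): √0.95 = 0.975 and √0.90 = 0.949. Simulation on patient-mean pain used 3,000 runs, an effect of 0.6 SD, two-sided alpha 0.05, race centred and no dropout. SEs are in SD units; both terms are added.

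| Share: sex / site | SE as written | SE adjusted | Change | Power, % |
|---|---|---|---|---|
| 0 / 0 | 0.2106 | 0.2145 | +1.9% | 80.1 → 79.2 |
| 2% / 2% | 0.2106 | 0.2103 | −0.1% | 81.2 → 80.6 |
| 5% / 5% | 0.2105 | 0.2032 | −3.5% | 81.2 → 83.4 |
| 10% / 10% | 0.2108 | 0.1916 | −9.1% | 82.0 → 86.8 |
| 5% / 0 | 0.2108 | 0.2092 | −0.8% | 79.6 → 79.0 |
| 0 / 10% | 0.2105 | 0.2033 | −3.4% | 80.1 → 82.3 |

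Adding sex alone in the 5%/5% row gives 0.2051, which is −2.6%, and power 82.3%. The range of about 2–9% and 1–5 points runs from there to the 10%/10% row. Monte Carlo SE for power is about 0.7 points.

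**4. Validity.** Mean estimates under the written model were 0.595–0.609 for a true 0.6. Its type I error was 3.4% in the 10%/10% setting (adjusted 4.2%), and 3.4–5.5% over all runs in which sex, site or both explained 5–10% (Monte Carlo SE about 0.4 points). The conservatism comes from sex. With 10%/10%, the model SE was 0.2106 under no effect but the estimates varied with SD 0.1988. With site alone at 10% the two agreed (0.2105 and 0.2097).

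**5. Interaction.** A separate simulation used strong site–race confounding (80/20), N = 90, 2,000 runs and a true β3 of −0.5. With site shifts of ±0.5, mean β3 was −0.52 without site terms and −0.51 with them. With shifts of ±1.0 it was −0.45 and −0.46 (Monte Carlo SE 0.02). The two models agree to 0.01, so omitting site is not what moves β3. Only β2 moved, to 0.6–1.1 against a true 0.

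**6. What the shares mean.** With an assumed patient SD of 2.0 and a half-and-half split, a sex gap of 2 × 2.0 × √(s/(1 − s)) gives share s: 0.92 NRS points for 5% and 1.33 for 10%. For site, the SD between hospitals is 2.0 × √(s/(1 − s)): 0.46 and 0.67.

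**The case against.** The strongest defence is that the blind review exists to add prognostic covariates, so the final model is not settled, and sex is already in secondary models. That is right, and it is why the point concerns the written model. But the review commits to no term. Section 4.3 also lists the study statistician among the unblinded roles, while 6.1 gives the review to the study statistician. That is a further reason to fix the terms beforehand.

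Next, nothing in the documents shows that sites differ. The capsules come from one compounding pharmacy, the single dose is observed, follow-up pain is collected by common REDCap surveys, and analgesic use is tracked for secondary analyses. This stands: the variance shares above are assumptions. So does the reminder that this is a pilot whose power figures 6.1 itself calls general estimates.

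The phrase in 4.3 about randomisation by the study site most naturally means that site staff operate the central service, but it could mean allocation within site. Clarification comes before any change to the algorithm.

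A reader might infer something stronger from the trial-wide race cap ("Once enrollment reaches 45 in a given race strata (e.g., non-Hispanic Black), enrollment for that race will cease"): that hospitals could differ in race mix, so site differences would contaminate the disparity test. The documents do not support this. That test is β3, and treatment is allocated 1:1 with race as a minimisation factor. A site difference therefore falls equally, in expectation, on both arms of each race. Uneven race mix shifts β2, from which 6.1 draws no conclusion. Bias in β3 would need treatment effects that differ by site as well as race mix that differs by site, and a site main effect would not remove it.

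**Conclusion.** The point holds as a modest matter of precision. The written primary pain model omits sex, which the design balances on, and site, and no text commits to adding either. If each explains 5–10% of between-patient variance, the SE of the treatment effect is about 2–9% larger than it need be, worth 1–5 points of power. The upper end needs sizeable differences: roughly 1.3 NRS points between the sexes and a between-hospital SD near 0.7, at a patient SD of 2.0. With shares of 2% the gain vanishes, and if neither factor matters adjustment costs about 2%.

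Neither β1 nor β3 is biased, and the error from omitting sex is in the conservative direction. A reader might work out a loss of up to 12% from site alone, as √((2.0² + 1.0²)/2.0²) = 1.118. That needs site to explain 1.0²/(2.0² + 1.0²) = 20% of variance, which no document supports. Nor does the omitted sex effect fall mainly into the visit-level error term: the patient intercept absorbs most of it, which still widens the SE of a between-patient contrast.

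**What to change.** **In 6.1:**
- Before the blind review, name sex and site (fixed or random) as terms in the primary pain model.
- State how ED pain score is handled: as an outcome, as now, or as a covariate with only the follow-up scores as outcomes.
- Report arm and race counts by site.

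**In 4.3:** say whether allocation is balanced within site. If it is not and enrolment is still open, site may be considered as a further minimisation factor. This is the secondary and more debatable request.

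**Cost:** the model change is SAP wording and remains possible until un-blinding, even if randomisation is complete. With four sites as fixed effects it uses 1 + 3 = 4 degrees of freedom out of 90 patients, and about 2% of the SE if neither factor matters. Adding site to the algorithm is a setting in the randomisation service. It loosens balance on the other factors slightly (mean worst sex difference 0.7 to 0.8 at assignment probability 1.0, and 1.6 to 1.8 at 0.8). It also calls for a stated random element, so that the next assignment is not predictable at a hospital with about 22 patients.
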